6.1. Critical Baseline Assessments

Disease, and therapy history, including cardiovascular medical history/risk factors will be assessed at Baseline. Investigators are encouraged to implement lifestyle modifications and adjust or initiate the appropriate pharmacotherapy throughout the study as recommended by current locally followed therapeutic cardiovascular and diabetes guidelines for participants in the study. Screening and randomisation can occur at the same visit depending on availability of information to determine eligibility of the subject to enter the study.

6.2. Safety

The following sections provide further detail on the safety assessments. Planned time points for all safety assessments are listed in the Time and Events Table ([Table 1](#)). Unscheduled visits will occur as medically necessary. Detailed procedures for obtaining each assessment are provided in the SRM.

Safety endpoints are described in [Section 2](#) and will include monitoring of cardiovascular events ([Section 6.2.1](#)), deaths, AEs of special interest ([Section 6.2.3](#)), clinically significant microvascular events ([Section 6.2.4](#)), SAEs and AEs leading to discontinuation of investigational product.

Liver chemistry stopping and follow-up criteria and AEs are described in [Section 4.4.3](#) and [Appendix 3](#).

6.2.1. Cardiovascular Events

Events referred to the CEC by the investigator as potential endpoints or transient ischemic attacks (TIAs) will not be collected or reported as SAEs, regardless of the adjudication outcome ([Section 6.2.2](#)). These events will be reviewed by an Independent Data Monitoring Committee ([Section 9.8](#)).

The CEC will review and adjudicate the following clinical events:

- Myocardial infarction
- Stroke
- Unstable angina requiring hospitalization
- Hospitalization for heart failure
- Sudden cardiac death
- TIA
- In addition, all clinical events submitted for adjudication and all other SAEs with a fatal outcome will be reviewed and adjudicated to classify the cause of death as cardiovascular or non-cardiovascular.

When the local investigator reported event and the CEC decision on the nature of the event differ, the CEC's decision will be considered final. The detailed descriptions of the endpoint (and TIA) definitions necessary for adjudication are contained within the CEC Charter (available on request). The guiding principle will be the "2014 ACC/AHA Key Data Elements and Definitions for Cardiovascular and Stroke End Point Events for Clinical Trials" [ACC/AHA, 2014] and the "Third Universal Definition of Myocardial Infarction" endorsed by the European Society of Cardiology (ESC), the American College of Cardiology Foundation (ACCF), the American Heart Association (AHA), and the World Heart Federation (WHF) [Thygesen, 2012].

Source documentation required to support the adjudication of the events is described in the SRM. Recording of potential endpoint and TIA events in the eCRF and submission of source documentation will be required for clinical events meeting reporting criteria whether or not an endpoint event is suspected by the investigator.

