2. OBJECTIVES AND ENDPOINTS

| Objectives | Endpoints |
|--|---|
| Primary | |
| To determine whether albiglutide is non-inferior with respect to MACE when added to glycaemic standard of care versus standard of care alone | 
 Time to first occurrence of MACE (cardiovascular death, myocardial infarction, or stroke) [Non-inferiority] |
| Secondary | |
| To supplement the primary objective by further characterization of the effects of albiglutide on cardiovascular outcomes | 
 Time to first occurrence of MACE [Superiority]^(1 see footnote) Time to first occurrence of the following: 
 MACE or urgent revascularisation for unstable angina The individual components of the primary endpoint Cardiovascular death or hospitalization due to heart failure |
| To evaluate the effects of albiglutide on metabolic management of type 2 diabetes | 
 Time to initiation of insulin of more than 3 months duration for those subjects not treated with insulin at study start ^(1 see footnote) Time to initiation of prandial insulin in those subjects on basal insulin at study start The proportion of subjects achieving glycaemic control (HbA1c ≤ 7.0% at final assessment) with no severe hypoglycaemic incidents and weight gain <5% of body weight ^(1 see footnote) The time to first occurrence of a clinically important microvascular event (see Section 6.2.4) Change in HbA1c Change in body weight Patient reported outcomes from TRIM-D/EQ5D |
| To evaluate the safety of albiglutide | 
 All cause mortality Non-fatal SAEs AEs leading to discontinuation of investigational product AE of special interest (see Section 6.2.3) Change in eGFR calculated using MDRD formula Change in blood pressure and heart rate |
| Exploratory | |
| To evaluate patient reported experience of diabetes treatment | 
 Patient reported outcomes from study specific questionnaire |

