6.2.2. Adverse Events (AE) and Serious Adverse Events (SAEs)

The definitions of an AE or SAE can be found in [Appendix 5](#).

The investigator or site staff will be responsible for detecting, documenting and reporting events that meet the definition of an AE or SAE.

For this study events of myocardial infarction, stroke, unstable angina requiring urgent revascularization, hospitalization for heart failure, TIA and sudden cardiac death will not be collected or reported as AEs or SAEs. These events will be collected separately, subjected to blinded adjudication by an independent CEC using prespecified diagnostic criteria, and reported separately (Section 6.2.1.1). All other events that meet serious criteria as defined in [Appendix 5](#) should be reported as SAEs.

All events with an outcome of death will be adjudicated to classify the cause of death as specifically cardiovascular or non-cardiovascular. Any event resulting in death should be reported as a SAE unless the event is myocardial infarction, stroke, unstable angina w/ urgent revascularization, Heart failure, TIA or sudden cardiac death which the protocol specifies are not to be collected as adverse events.

The study will not collect all non-serious AEs. Non-serious AEs leading to discontinuation of investigational product and non-serious AEs of special interest (see Section 6.2.3) will be collected.

Any events not specifically addressed above should be reported as an AE or SAE according to the definitions in [Appendix 5](#).

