11.5.2. Definition of Serious Adverse Events

If an event is not an AE per definition above, then it cannot be an SAE even if serious conditions are met (e.g., hospitalization for signs/symptoms of the disease under study, death due to progression of disease, etc).

Serious Adverse Event (SAE) is defined as any untoward medical occurrence that, at any dose:

c. Results in death**d. Is life-threatening**

NOTE:

The term 'life-threatening' in the definition of 'serious' refers to an event in which the subject was at risk of death at the time of the event. It does not refer to an event, which hypothetically might have caused death, if it were more severe.

e. Requires hospitalization or prolongation of existing hospitalization

NOTE:

- In general, hospitalization signifies that the subject has been detained (usually involving at least an overnight stay) at the hospital or emergency ward for observation and/or treatment that would not have been appropriate in the physician's office or out-patient setting. Complications that occur during hospitalization are AEs. If a complication prolongs hospitalization or fulfils any other serious criteria, the event is serious. When in doubt as to whether "hospitalization" occurred or was necessary, the AE should be considered serious.
- Hospitalization for elective treatment of a pre-existing condition that did not worsen from baseline is not considered an AE.

f. Results in disability/incapacity

NOTE:

- The term disability means a substantial disruption of a person's ability to conduct normal life functions.
- This definition is not intended to include experiences of relatively minor medical significance such as uncomplicated headache, nausea, vomiting, diarrhoea, influenza, and accidental trauma (e.g. sprained ankle) which may interfere or prevent everyday life functions but do not constitute a substantial disruption

g. Is a congenital anomaly/birth defect**h. Other situations:**

- Medical or scientific judgment should be exercised in deciding whether reporting is appropriate in other situations, such as important medical events that may not be immediately life-threatening or result in death or hospitalization but may jeopardize the subject or may require medical or surgical intervention to prevent one of the other outcomes listed in the above definition. These should also be considered serious.

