6.2.1. Cardiovascular Events

Events referred to the CEC by the investigator as potential endpoints or transient ischemic attacks (TIAs) will not be collected or reported as SAEs, regardless of the adjudication outcome ([Section 6.2.2](#)). These events will be reviewed by an Independent Data Monitoring Committee ([Section 9.8](#)).

The CEC will review and adjudicate the following clinical events:

- Myocardial infarction
- Stroke
- Unstable angina requiring revascularization
- Hospitalization for heart failure
- Sudden cardiac death
- TIA
- In addition, all clinical events submitted for adjudication and all other SAEs with a fatal outcome will be reviewed and adjudicated to classify the cause of death as cardiovascular or non-cardiovascular.

When the local investigator reported event and the CEC decision on the nature of the event differ, the CEC's decision will be considered final. The detailed descriptions of the

endpoint (and TIA) definitions necessary for adjudication are contained within the CEC Charter (available on request). The guiding principle will be the “2014 ACC/AHA Key Data Elements and Definitions for Cardiovascular and Stroke End Point Events for Clinical Trials” [ACC/AHA, 2014] and the “Third Universal Definition of Myocardial Infarction” endorsed by the European Society of Cardiology (ESC), the American College of Cardiology Foundation (ACCF), the American Heart Association (AHA), and the World Heart Federation (WHF) [Thygesen, 2012].

Source documentation required to support the adjudication of the events is described in the SRM. Recording of potential endpoint and TIA events in the eCRF and submission of source documentation will be required for clinical events meeting reporting criteria whether or not an endpoint event is suspected by the investigator.

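### Sections 6.2.1 and 6.2.2 conflict on whether a hospital admission for unstable angina without urgent revascularisation is reported as an SAE

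*Protocol*

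**What the plan says.** Section 6.2.1 sets its exemption by referral: events sent to the CEC as potential endpoints or TIAs "will not be collected or reported as SAEs, regardless of the adjudication outcome". The list of events the CEC adjudicates follows in the same section and includes "Unstable angina requiring hospitalization".

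Section 6.2.2 sets its exemption by diagnosis. Besides myocardial infarction and stroke, it states that "unstable angina requiring urgent revascularization, hospitalization for heart failure, TIA and sudden cardiac death will not be collected or reported as AEs or SAEs". The residual rule follows: "All other events that meet serious criteria as defined in" Appendix 5 are to be reported as SAEs. A later sentence in 6.2.2, on events with a fatal outcome, gives the exempt events again, this time as myocardial infarction, stroke, "unstable angina w/ urgent revascularization, Heart failure, TIA or sudden cardiac death".

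Appendix 5 (Section 11.5.2) makes an event serious if it "Requires hospitalization or prolongation of existing hospitalization". Section 2 lists "Non-fatal SAEs" among the endpoints for the safety objective.

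**The concern.** The two sections are meant to state one rule, since the exemption sentence in 6.2.1 itself points to 6.2.2. They give different answers for one common kind of admission in a population with established cardiovascular disease.

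Two sites could handle the same admission differently, each following the protocol as written. One would refer it to the CEC and enter no SAE. The other would enter an SAE, with the 24-hour report (Section 6.2.2.1) and the causality assessment (Appendix 5) that go with it. The non-fatal SAE count, and the tables by system organ class and preferred term in Section 8.3.6.4, would then mix two definitions.

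**Working it through.** No stated figure depends on this point, so the check is a comparison of texts. Sections 6.2.1 and 6.2.2 are both read in the full Amendment 1 protocol, so neither is superseded relative to the other.

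**Step 1: is the event serious?** An admission for unstable angina meets the hospitalisation criterion of Section 11.5.2. Yes.

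**Step 2: apply each section.**

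| Event | Section 6.2.1, once referred to the CEC | Section 6.2.2 | Agree? |
|---|---|---|---|
| Unstable angina, admitted, urgent revascularisation | Not an SAE | Not an SAE (on the list) | Yes |
| Unstable angina, admitted, no urgent revascularisation | Not an SAE (type is on the CEC list) | SAE (not on the list, serious) | **No** |

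**Step 3: the fatal-event sentence of 6.2.2.** For unstable angina it keeps the narrow form, with urgent revascularisation, so it does not match 6.2.1 either. For heart failure it is broader than the first list in the same section: heart failure without qualification, against hospitalisation for heart failure. A death from heart failure with no admission is exempt under the fatal-event sentence and reportable under the first list plus the residual rule. This second slip concerns fatal events, so it does not alter the non-fatal count.

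**Step 4: how the mismatch arose.** In the original protocol the CEC list in 6.2.1 read "Unstable angina requiring revascularization", close to the wording of 6.2.2. Amendment 1 replaced it with the hospitalisation wording. Its list of specific changes covers 6.2.1 and does not mention 6.2.2. The Amendment 2 log adds a footnote to the exemption sentence of 6.2.1 for Mexico and lists no change to 6.2.2. The body of those sections under Amendment 2 is not shown, so its state is inferred from the log.

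**Step 5: the cross-reference.** Section 6.2.2 says that the adjudicated events are handled under Section 6.2.1.1. That section covers other cardiovascular events; the adjudicated events are in 6.2.1.

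**Step 6: what is and is not touched.** The primary endpoint is adjudicated cardiovascular death, myocardial infarction or stroke. Unstable angina is not a component, and adjudication does not depend on SAE status. The primary analysis and its 611-event target are unchanged.

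**The case against.** The best defence is that the sections can be read together. The list in 6.2.1 is formally an adjudication list, and the exemption sentence covers only events referred as potential endpoints, with TIA named separately. The unstable angina endpoint in Section 2 is urgent revascularisation, the same concept as in 6.2.2. On that reading the CEC screens all unstable angina admissions, and only those with urgent revascularisation are exempt. The reason given for the Amendment 1 change, to match the CEC's review process, fits this.

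The reading is possible, but the protocol does not state it. The exemption in 6.2.1 turns on referral, and that section asks for submission of qualifying events whether or not the investigator suspects an endpoint. The Amendment 2 footnote presents SAE submission of every event referred by Mexican investigators as the one exception, which implies that referred events elsewhere are all exempt. A site could reasonably follow either section.

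A reader might also infer that serious events refuted by the CEC are lost to safety review. The documents do not support that. Exempting them whatever the adjudication outcome is an explicit choice, kept when Amendment 2 reopened the sentence. These events are recorded in the eCRF, reviewed by the IDMC and summarised separately under Section 8.3.6.4. The Amendment 2 log does shorten that summary, striking the results by event type and treatment group and the by-subject listing, but table layout may be settled in the analysis plan, which is not shown.

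It also stands that blinding makes it unlikely that sites' choices differ by arm, and that non-fatal SAEs are not formally tested.

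**Conclusion.** The conflict on hospitalised unstable angina without urgent revascularisation is real and sits in current text. Its effect is confined to SAE data: the non-fatal SAE endpoint has no single definition for this event type, and its count will vary with the section each site follows. The conclusion rests on two assumptions: that sites refer such admissions to the CEC, as the adjudication list directs, and that the body of Amendment 2 matches its log.

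No number can be attached. The documents give neither the expected number of unstable angina admissions, nor the share without urgent revascularisation, nor a CEC confirmation rate, so any count of misplaced events would only reflect what was assumed. A systematic difference between arms is not shown.

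The point is worth correcting because it is specific and cheap. It does not threaten the primary conclusion.

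**What to change.** - Reconcile Section 6.2.1, the first list in 6.2.2 and the fatal-event sentence of 6.2.2 to one identical list of events exempt from SAE reporting, covering both unstable angina and heart failure. Which definition to adopt is for the sponsor; what matters is that all three places agree.
- Correct the cross-reference in 6.2.2 from 6.2.1.1 to 6.2.1.
- For data already collected, compare unstable angina referrals to the CEC with the SAE records and apply one rule to both when the SAE tables are built.
- As an analysis step, tabulate by treatment group, beside the SAE tables, the CEC-referred serious events that were not confirmed. Use the existing eCRF and CEC data. Sites should not have to enter these as SAEs after adjudication, which would sit badly with the 24-hour reporting rule.

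The cost is a few sentences in an amendment, a note to sites, and programming for one comparison and one table. The by-subject listing planned under Amendment 1 was to show seriousness for events sent to the CEC, so the field needed for the table appears to be collected.

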6.2.1.1. Other CV Events

GSK has identified other CV events of special interest for all clinical studies. Investigators will be required to fill out event specific data collection tools for the following cardiovascular events which meet SAEs criteria or are non-serious events that result in discontinuation of investigational product:

- Arrhythmias (other than atrial fibrillation/flutter, see Section 6.2.3)
- Valvulopathy
- Pulmonary hypertension
- Peripheral arterial thromboembolism
- Deep venous thrombosis/pulmonary embolism
- Revascularisation (other than urgent revascularisation for unstable angina, a component of a secondary endpoint)

This information should be recorded in the specific cardiovascular eCRF within one week.

6.2.2. Adverse Events (AE) and Serious Adverse Events (SAEs)

The definitions of an AE or SAE can be found in [Appendix 5](#).

The investigator or site staff will be responsible for detecting, documenting and reporting events that meet the definition of an AE or SAE.

For this study events of myocardial infarction, stroke, unstable angina requiring urgent revascularization, hospitalization for heart failure, TIA and sudden cardiac death will not be collected or reported as AEs or SAEs. These events will be collected separately, subjected to blinded adjudication by an independent CEC using prespecified diagnostic criteria, and reported separately (Section 6.2.1.1). All other events that meet serious criteria as defined in [Appendix 5](#) should be reported as SAEs.

All events with an outcome of death will be adjudicated to classify the cause of death as specifically cardiovascular or non-cardiovascular. Any event resulting in death should be reported as a SAE unless the event is myocardial infarction, stroke, unstable angina w/ urgent revascularization, Heart failure, TIA or sudden cardiac death which the protocol specifies are not to be collected as adverse events.

The study will not collect all non-serious AEs. Non-serious AEs leading to discontinuation of investigational product and non-serious AEs of special interest (see Section 6.2.3) will be collected.

Any events not specifically addressed above should be reported as an AE or SAE according to the definitions in [Appendix 5](#).

6.2.2.1. Time period and Frequency for collecting AE and SAE information

- AEs and SAEs will be collected from the start of Study Treatment until the follow-up contact (see Section 6.2.2.3), at the timepoints specified in the Time and Events Table ([Table 1](#)).
- Medical occurrences that begin prior to the start of study treatment but after obtaining informed consent may be recorded on the Medical History/Current Medical Conditions section of the eCRF.
- Any SAEs assessed as related to study participation (e.g., protocol-mandated procedures, invasive tests, or change in existing therapy) or related to a GSK product will be recorded from the time a subject consents to participate in the study up to and including any follow-up contact.
- All SAEs will be recorded and reported to GSK within 24 hours, as indicated in [Appendix 5](#).
- Investigators are not obligated to actively seek AEs or SAEs in former study subjects. However, if the investigator learns of any SAE, including a death, at any time after a subject has been discharged from the study, and he/she considers the event reasonably related to the study treatment or study participation, the investigator must promptly notify GSK.

NOTE: The method of recording, evaluating and assessing causality of AEs and SAEs plus procedures for completing and transmitting SAE reports to GSK are provided in [Appendix 5](#).

6.2.2.2. Method of Detecting AEs and SAEs

Care will be taken not to introduce bias when detecting SAEs. Open-ended and non-leading verbal questioning of the subject is the preferred method to inquire about SAE occurrence. Appropriate questions include:

- “How are you feeling?”
- “Have you had any (other) medical problems since your last visit/contact?”

- “Have you taken any new medicines, other than those provided in this study, since your last visit/contact?”

Additionally subjects will be asked specific questions about the occurrence of AEs of special interest (Section 6.2.3).

6.2.2.3. Follow-up of AEs and SAEs

After the initial AE/SAE report, the investigator is required to proactively follow each subject at subsequent visits/contacts. All SAEs, and non-serious AEs of special interest (as defined in Section 6.2.3) will be followed until resolution, until the condition stabilizes, until the event is otherwise explained, or until the subject is lost to follow-up (as defined in Section 4.5). Further information on follow-up procedures is given in [Appendix 5](#).

6.2.2.4. Sentinel Events

A Sentinel Event is a GSK-defined SAE that is not necessarily drug-related but has been associated historically with adverse reactions for other drugs and is therefore worthy of heightened pharmacovigilance. Medical monitor review of all SAEs for possible Sentinel Events is mandated at GSK. The GSK medical monitor may request additional clinical information on an urgent basis if a possible Sentinel Event is identified on SAE review. The current GSK-defined Sentinel Events are listed below:

- Acquired Long QT Syndrome
- Agranulocytosis/severe neutropenia
- Anaphylaxis and anaphylactoid reactions (see also Section 6.2.3)
- Hepatotoxicity (see also Section 6.2.3)
- Acute renal failure
- Seizure
- Stevens Johnson syndrome/toxic epidermal necrosis

